6.3 Concomitant Therapy

Prior to week 12, lipid-regulating concomitant medications should not be altered, unless there is a clinically compelling reason for change. The investigator must contact the Amgen medical monitor to discuss such cases on an individual basis. After week 12, investigators may prescribe any concomitant medications or treatments deemed necessary to provide adequate supportive care except for those listed in [Section 6.4](#). If needed, apheresis will be permitted at any time during the study.

[figure not shown]

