7. STUDY PROCEDURES

This will be a multicenter, open-label study to assess the long-term safety, tolerability, and efficacy of AMG 145. For the purpose of this study, a month is defined as 4 weeks and a quarter is defined as 12 weeks.

Subjects that fall within a 1 month window of completing a qualifying parent study do not require screening procedures to be performed; they may be enrolled into the study directly, as outlined in [Section 7.1.2](#). All other subjects must go through the study screening procedures as outlines in [Section 7.1.1](#).

Written informed consent must be obtained and will be implemented before protocol specific procedures are carried out. The risks and benefits of participating in the study will be verbally explained to each potential subject prior to entering into the study. The procedures to be performed at each clinic visit are described below and are summarized in [Appendix A](#). Subjects must be fasting for ≥ 9 hours before each study visit where labs are collected. IP should not be administered until all study procedures are completed at each visit. Blood draws for subjects on apheresis (main study and sub-study) will need to occur both before and after apheresis

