#### 6. Definitions

The study consists of four different types of subjects,

- Homozygous FH Apheresis Subjects: Subjects who either met clinical criteria
  of HoFH or who had supportive genetic information; and receiving apheresis at
  study baseline.
- Homozygous FH Non-Apheresis Subjects: Subjects who either met clinical criteria of HoFH or who had supportive genetic information; and not receiving apheresis at study baseline
- Severe Heterozygous FH Apheresis Subjects: Subjects who didn't meet clinical criteria of Homozygous FH and who had supportive genetic information; and receiving apheresis at study baseline
- Severe Heterozygous FH Non-Apheresis Subjects: Subjects who didn't meet clinical criteria of Homozygous FH and who had supportive genetic information; and not receiving apheresis at study baseline

Some of the definitions will depend on the subject type.

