#### 10. Statistical Methods of Analysis

## 10.1 General Principles

Statistical analyses in this open label, single arm study are descriptive in nature. No statistical inference or missing value imputation is planned. Subject disposition, demographics and baseline characteristics will be summarized.

Summary statistics for continuous variables will include the number of subjects, mean, median, standard deviation or standard error, 25th percentile (Q1), 75th percentile (Q3), minimum, and maximum. For categorical variables, the frequency and percentage will be given.

Final analyses will be based on data collected from this study. Descriptions of any integrated analyses with the parent studies are out of scope for this study.

The final analysis for the study will be performed at the end of the study (defined as when the last subject has completed the assessments for week 260 or until the investigator's recommendation of discontinuation, Amgen's recommendation of discontinuation, the subject's decision to discontinue for any reason, or until an administrative decision is made to close the study). At that time, the database will be cleaned, processed and locked. All endpoints will be analyzed based on this snapshot.

For the interim analysis, subjects were summarized by the 20110233 parent rollover/non-20110233 parent rollover and assigned treatment groups in 20110233 (AMG 145 or placebo) if applicable. However, for the final analysis, subjects will be summarized based only on the apheresis status at **enrollment** when applicable described in section 6.3.

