#### 10.6.6 Apheresis Summaries

For all the subjects who were treated by apheresis at least once during the study, the number and proportion of subjects will be summarized by the type of change (**change in method of apheresis**, change in frequency, change in method, discontinuation of apheresis, first-time initiation of apheresis, re-initiation of apheresis, missed/skipped apheresis procedure and **other**) and primary reason of change.

Statistical Analysis Plan: 20110271

Dated: 26 May 2018 Page 20 of 27

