#### Handling multiple records assigned to an analytical study week:

If there is more than one record in a study week interval, the analytical record for that specific study week will be defined as followings:

The record closest to the scheduled study day of the specific study week (7\*study week+1) will be selected. If two records are equidistant from the scheduled day, then the earlier record will be chosen. If there are multiple records on the same day, the last record will be used.

Handling multiple records assigned to an analytical study week for apheresis patients:

For apheresis patients, their apheresis date is aligned with the scheduled visit. As such, when multiple records available during a visit window, the one on the same day as apheresis should be selected. If no apheresis record can be found during the visit window, then the records will be mapped using the target visit date instead. If both pre-and post-apheresis assessments were performed, the pre-apheresis assessment will be used for summary for the sake of this SAP.

Statistical Analysis Plan: 20110271

Dated: 26 May 2018 Page 24 of 27

Table A.1 Visit Windows for Labs, hsCRP, Antibodies and Vitamin E

		Chemistry,			
		Coagulation,			
	Scheduled	Hematology,			
Scheduled	Visit Study	hsCRP,	Anti-AMG 145	Direct LDL,	Fasting Vitamin
Visit Week	Day	HbA1c	antibodies	Direct VLDL	E
Week 4	29			2-42	
Week 6	43				
Week 8	57			43-70	
Week 12	85	2-126	2-126	71-98	2-126
Week 16	113			99-126	
Week 20	141			127-154	
Week 24	169	127-210	127-210	155-210	127-210
Week 36	253	211-294	211-294	211-294	211-294
Week 48 / Year 1	337	295-378	295-504	>=295	295-420
Week 60	421	379-462			
Week 72	505	463-546			421-588
Week 84	589	547-630			
Week 96 / Year 2	673	631-714	505-882		>=589
Week n	n*7+1	From (n-6)*7+1 to (n+6)*7			
Week 156 / Year 3	1093		883-1260		
Week 204 / Year 4	1429		1261-1638		
Week 264 / Year 5	1849	an ingramantal h	>=1639		

Where n = 108, 120, 132 and so on, incremental by 12, until 264

Statistical Analysis Plan: 20110271

Dated: 26 May 2018 Page 25 of 27

Table A.2 Visit Window for Vital Signs, Lipid Labsa, Lp(a) PK and PCSK9

		Vital Signs, Fasting plasma lipids a , ApoA1, ApoB, Lp(a), PK, PCSK9		
Scheduled Visit Week	Scheduled Visit Study Day	Parent Study Rollover	Non-Parent / Non-Apheresis	Non-Parent / Apheresis
Week 2	15			2-21
Week 4	29	2-35	2-35	22-35
Week 6	43	36-49	36-49	36-49
Week 8	57	50-70	50-70	50-60
Week 9	64			61-67
Week 10	71			68-77
Week 12	85	71-98	71-98	78-98

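### SAP Appendix A does not say which same-day record rule covers subjects who start apheresis on study, and one natural reading selects their post-apheresis LDL-C

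*SAP*

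**What the plan says.** SAP Appendix A, on multiple records in a study week, first picks the record nearest the scheduled day and then settles same-day duplicates: "If there are multiple records on the same day, the last record will be used". A separate paragraph follows for apheresis patients. It opens with "For apheresis patients, their apheresis date is aligned with the scheduled visit", prefers the record from the apheresis day, and ends: "If both pre-and post-apheresis assessments were performed, the pre-apheresis assessment will be used for summary for the sake of this SAP". The appendix does not say whether an apheresis patient is someone on apheresis at baseline or someone on apheresis at the time of the visit.

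Elsewhere the SAP fixes apheresis status at the start. Section 6 defines the non-apheresis types as "not receiving apheresis at study baseline", and the apheresis types in the matching way. The study cohorts in Section 6.3 are by status at baseline. Section 10.1 says that in the final analysis "subjects will be summarized based only on the apheresis status at" enrollment.

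Subjects who start later are foreseen. Protocol Section 6.3 states: "If needed, apheresis will be permitted at any time during the study". SAP Section 10.6.6 tabulates "first-time initiation of apheresis" as a type of change. Protocol Section 7 says that blood draws for subjects on apheresis "will need to occur both before and after apheresis".

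**The concern.** On a day with paired draws, the last record is normally the post-apheresis one. The two rules therefore give opposite answers for the same sampling situation, and the plan does not say which one governs a subject who began apheresis after enrollment.

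The endpoints at stake are secondary: LDL-C percent change at each visit, and the proportion with a reduction of 15% or more. Protocol Section 2.1 describes apheresis as physical removal of LDL cholesterol with a transient effect, so the two samples are not interchangeable. If the post-apheresis value were used for a starter in the cohort not on apheresis at baseline, the removal would be read as response to AMG 145. There is no control group against which such a shift would show.

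**Working it through.** The plan gives no figure on this point to reproduce. The check is a reading of the rules, followed by an illustration with assumed values.

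**Step 1. Which rule covers a starter?**

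For the baseline-status reading:
- SAP Section 6 sets subject type at study baseline and adds that subject type governs some of the other definitions.
- Table A.2 sorts lipid records into fixed columns: parent rollover, non-parent without apheresis, and non-parent with apheresis. A starter has no apheresis column.
- The pre-apheresis paragraph rests on apheresis being aligned with visits. Protocol Appendix A states that alignment only in the schedule for apheresis subjects.
- Where the SAP means anyone treated with apheresis even once on study, it says so (Section 10.6.6). Appendix A does not.

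For the current-status reading:
- The term carries no baseline qualifier in Appendix A, although the SAP adds one in several other places.
- The final sentence of the paragraph is triggered by the existence of both assessments, which a starter can have.

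Both readings are open. The first follows the SAP's only definitions.

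**Step 2. What must happen for the wrong sample to be used?**

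Three conditions must all hold:
1. The baseline-status reading is programmed.
2. A session falls on the day whose record is selected.
3. A post-session sample is drawn and is the last record that day.

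**Step 3. Illustration.** Let d be the true LDL-C change on drug, r the acute fractional removal in the session, and s the share of the cohort with a post-apheresis record selected at that visit. None of the three comes from the documents. All are assumptions.

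Apparent change = 100 × [(1 + d)(1 − r) − 1].

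| r | d = 0 | d = −20% |
|---|---|---|
| 20% | −20% | 0.80 × 0.80 − 1 = −36% |
| 40% | −40% | 0.80 × 0.60 − 1 = −52% |
| 60% | −60% | 0.80 × 0.40 − 1 = −68% |

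Removal that alone reaches the 15% threshold: r = 1 − 0.85/(1 + d). This is 15% at d = 0, 10.5% at d = −5% and 5.6% at d = −10%.

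Shift in the cohort mean = s × (apparent change − d). With d = −20%, the shift per affected subject is −16 points at r = 20% and −48 points at r = 60%.
- Smallest case: 0.01 × (−16) = −0.16, so the mean moves from −20% to about −20.2%.
- Largest case: 0.10 × (−48) = −4.8, so the mean moves from −20% to −24.8%.

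The response rate can rise by at most s, and only through starters whose true reduction is below 15%. A starter at a true −20% is already a responder.

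If the pre-apheresis record is used, r for that session drops out and the apparent change returns to d, apart from any carry-over from earlier sessions.

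**The case against.** The strongest reply is that no sentence in the SAP assigns starters to the last-record rule. The specific paragraph comes directly after the general one, and its closing sentence turns on whether both samples were taken. Grouping the tables by enrollment status does not by itself decide which sample is selected. A sensible programmer could already be doing the right thing. This stands, and it is why the point is about an undefined term with a harmful reading rather than about a rule that is wrong on its face.

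It is also fair that paired samples in starters are not assured. The protocol's schedules for rollover and non-apheresis subjects do not mention paired draws. Section 7 does require them for subjects on apheresis, but it also still refers to a sub-study, and Amendment 3 lists the apheresis substudy as removed. After week 24 the routine visits are 12 weeks apart, so a session need not fall on a visit day. This limits how often the problem can arise but does not remove it.

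Two wider inferences are not supported. A reader might infer that the error favours the drug for every analyte. For LDL-C the direction is clear, but a lower AMG 145 concentration after a session would not flatter the drug, and SAP Section 10.6.3 has the effect of apheresis on AMG 145 and PCSK9 examined separately. A reader might also extend the point to baseline values of rollover subjects, because SAP Section 6.1 states its pre-apheresis baseline rule only for non-parent apheresis subjects. A first-time starter has no pre/post pair at baseline, and nothing in the documents shows paired apheresis baselines in the parent studies.

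**Conclusion.** The gap is real. Appendix A holds two opposite same-day rules and leaves open which one applies to a group that both documents foresee. Under the SAP's own baseline definitions, a starter with paired draws on the selected day would contribute a post-apheresis LDL-C to the secondary endpoints, with an error toward a larger apparent reduction.

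The size cannot be fixed from the documents. The range of about −0.2 to −4.8 points in the cohort mean rests on assumed removal of 20-60%, 1-10% of the cohort affected at a visit and a true change of −20%. It applies only if all three conditions in the working hold. The effect may be small for the cohort and large for the individual.

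It would go too far to say that the SAP directs post-apheresis values to be used for starters, since the text can be read either way. The primary endpoint, adverse events, is not touched, and no inference is planned. The point merits correction because one reading gives a wrong endpoint value and the repair is simple.

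**What to change.** In SAP Appendix A, attach the rule to the sample instead of the subject's label. Whenever pre- and post-apheresis samples exist on the same day, in any subject and regardless of apheresis status at baseline, use the pre-apheresis record. State that the last record of the day applies only where there is no such pair.

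The cost is one sentence in the SAP and one programming condition on the pre/post sample label. No new data are needed, and the change agrees with what the SAP already does for apheresis patients. It removes only the same-session effect. Carry-over from earlier sessions in starters remains and should be acknowledged when the by-visit results are described.

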Central Laboratory						
Blood draws (lipids, PCSK9, and PK) will be collected both before and after apheresis						
Fasting plasma lipids, Lp(a), ApoA1, ApoB ^d	X	X	X	X ^e	X	X
PK samples (AMG 145), PCSK9	X ^g	X ^g	X	X ^e	X	X
Chemistry	X		X		X	X
Hematology	X		X		X	X
HbA1c	X		X		X	X
Coagulation	X		X		X	X
hsCRP			X		X	X
Fasting Vitamin E			X ^h		X ^h	X
Biomarkers (blood)			X		X ⁱ	
Anti-AMG 145 antibodies			X		X ^j	X
Serum pregnancy (females of childbearing potential) and FSH		X ^{k,l}	X ^k		X ^l	X
Urinalysis, eGFR	X ^m		X			X
Investigational Product						
IP administration, QM or Q2W ⁿ			X	X	X	

Footnotes defined on the next page.

- a All apheresis subjects must have their apheresis schedule aligned with the Q2W dosing of AMG 145. In addition, week -2 screening should happen on an apheresis day. Week -1 should not occur on an apheresis day. Screening procedures may occur at any time during the 6 week screening window, with the exception of lipids labs, which need to be drawn both at week -2 and week -1.
- b D1 = day of first administration of investigational product (AMG 145 Q2W).
- c Quarterly visits will start at week 12 and occur every 12 weeks thereafter. Starting at week 24, all subjects will have the option of self-administering AMG 145. Prior to week 24, subjects that are treated with AMG 145 420 mg administered SC Q2W will have to self-administer study drug between some visits or visit the site. Visits should still coincide with apheresis sessions and AMG 145 should be provided after (but on the same day) as apheresis.
- d Investigators and staff involved with this trial should remain blinded to locally obtained lipid panels until the week 8 visit for all subjects that transition from an ongoing blinded (or blinded portion) parent study into this study, in order to avoid potential unblinding of the ongoing parent study.
- e Weeks -2, -1, 2, 4, 6, 8, 9, 10, 16 and 20 labs are mandatory for apheresis subjects.
- g PCSK9 only.
- h Vitamin E will only be collected at EOS Parent/Day 1 and at weeks 12, 24, 48 (year 1), 72, and 96 (year 2) .
- l Biomarkers will only be collected at month 3 (week 12).
- j After year 1 antibody samples will only be collected at the end of each year.
- k FSH = in applicable subjects for study entry only – see [exclusion criteria](#).

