#### 10.7 Other Safety Analyses

#### 10.7.1 Laboratory Test Results

Descriptive statistics will be provided for actual values and changes from baseline in each laboratory parameter at each protocol-specified scheduled visit. Laboratory analytes are provided in the protocol Table 3. Lab shift tables using the most current version of the CTCAE version 4.0 (Appendix B) grading will be used for the following analytes of interest:

- Glucose (hypoglycemia and hyperglycemia)
- Total bilirubin (blood bilirubin increased)
- ALP (alkaline phosphatase increased)
- AST (SGOT) (aspartate aminotransferase increased)
- ALT (SGPT) (alanine aminotransferase increased)
- INR (INR increased)
- Platelets (platelet count decreased)
- WBC/Leukocytes (white blood cell decreased and leukocytosis)
- Neutrophils (neutrophil count decreased)

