Week 16	113	99-126	99-126	99-126
Week 20	141	127-154	127-154	127-154
Week 24	169	155-210	155-210	155-210
Week n	n*7+1	From (n-6)*7+1 to (n+6)*7	From (n-6)*7+1 to (n+6)*7	From (n-6)*7+1 to (n+6)*7

Where n=36, 48, 60 and so on, incremental by 12, until 264. a Lipid panel excluding Direct VLDL and Direct LDL.

Table A.3 Visit Window for Endpoints Collected only at the End of Study

Scheduled Visit Week	Weight, Physical Exam, Urinalysis, 12 Lead ECG,eGFR
EOS	>1

Statistical Analysis Plan: 20110271

Dated: 26 May 2018 Page 26 of 27

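### SAP Appendix A has no end-of-study window for fasting vitamin E, so every sample from day 589 on maps to week 96; the last visit is also labelled week 264 instead of week 260

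*SAP*

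**What the plan says.** **Collection.** Protocol 7.1.2.6 lists fasting vitamin E among the blood draws at the end-of-study (week 260) or early-termination visit for all subjects. The EOS/ET cell for vitamin E is marked, without a footnote letter, in all three Appendix A schedules. A footnote attached to the Day 1 and quarterly cells of the same row limits vitamin E to Day 1 and weeks 12, 24, 48, 72 and 96.

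**Planned summary.** SAP 10.7.1 calls for actual values and "changes from baseline in each laboratory parameter at each protocol-specified scheduled visit", and adds that "Laboratory analytes are provided in the protocol Table 3". Protocol Table 3 includes fasting vitamin E.

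**Windows.** SAP Table A.1, "Visit Windows for Labs, hsCRP, Antibodies and Vitamin E", gives vitamin E its own column. The last entry is week 96, day 589 or later, with no upper limit and no later row. Table A.3, "Visit Window for Endpoints Collected only at the End of Study", covers "Weight, Physical Exam, Urinalysis, 12 Lead ECG,eGFR" and nothing else.

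**Choice among several records.** The general rule selects "The record closest to the scheduled study day of the specific study week". For apheresis patients a separate paragraph says that "the one on the same day as apheresis should be selected", and it falls back on the target date only if the window holds no apheresis-day record.

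**Last visit.** The notes to Tables A.1 and A.2 step by 12 weeks up to week 264 (day 1849). SAP 3.1 and 10.1 and protocol 7.1.2.6 end the study at week 260.

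**The concern.** An open last window is harmless when nothing is scheduled after it. Here a further vitamin E draw is scheduled at week 260, and the SAP gives it no window of its own. Followed literally, the SAP sends every vitamin E record from day 589 on to week 96.

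- **Non-apheresis subjects.** The later value is discarded if a record closer to day 673 exists. If none exists, it is reported as week 96.
- **Apheresis subjects.** An end-of-study sample taken on an apheresis day would displace a valid week 96 sample that was not. If both fall on apheresis days, which the protocol intends ("Visits should still coincide with apheresis sessions", apheresis schedule, footnote c), the apheresis paragraph does not say which to take.

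What is at stake is the only vitamin E measurement scheduled after week 96 in a long-term safety study, and possible contamination of the week 96 summary. Separately, the final-visit tables would carry a week that the protocol does not have.

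**Working it through.** **Inputs.** Target day = 7 × week + 1 (SAP Appendix A). Week-n window = (n − 6) × 7 + 1 to (n + 6) × 7 (Tables A.1 and A.2). Vitamin E windows and the week 264 row come from Table A.1; the week 260 final visit comes from protocol 7.1.2.6.

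**1. Reproducing the SAP's figures.**
- Week 72: 7 × 72 + 1 = 505. Week 96: 673. Week 204: 1429. Week 264: 1849. All agree with Table A.1.
- Lower bound of the week 96 vitamin E window: (505 + 673)/2 = 589. This agrees, and shows that the cut-points are midpoints with the midpoint day given to the later visit.

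**2. Where an end-of-study vitamin E sample goes.**
- Week 260: 7 × 260 + 1 = day 1821.
- Since 1821 ≥ 589, it falls in week 96.
- Distance from target: 1821 − 673 = 1148 days; 1148/7 = 164 weeks; 1148/365.25 = 3.1 years.
- A week 96 sample taken within the protocol's ±7 days lies on days 666 to 680, at most 7 days from target. The closest-record rule therefore keeps it and drops the day 1821 value. Without a nearer record, the day 1821 value becomes the week 96 value.
- Early-termination samples before day 589 go to earlier windows: day 300 to week 48 (295–420), day 500 to week 72 (421–588). The week 96 problem concerns day 589 onward only.

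**3. The final-visit label.**
- Week 252 window: 246 × 7 + 1 = 1723 to 258 × 7 = 1806.
- Week 264 window: 258 × 7 + 1 = 1807 to 270 × 7 = 1890.
- Week 260 ± 7 days: 1814 to 1828, wholly inside 1807–1890, so no on-time value is lost.
- Target shift: 1849 − 1821 = 28 days.
- For antibodies, day 1821 falls in the Year 5 window (day 1639 onward), again under the week 264 label.

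**4. Replacement cut-points, by the SAP's midpoint convention.**
- Upper limit for week 96 vitamin E, keeping the 24-week spacing (week 120 = day 841): (673 + 841)/2 − 1 = 756.
- Week 252 (day 1765) against week 260: (1765 + 1821)/2 = 1793.
- Antibody Year 4 (day 1429) against week 260: (1429 + 1821)/2 = 1625.

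**The case against.** The strongest reply is that no end-of-study vitamin E sample was intended. The footnote restricts collection to Day 1 and weeks 12 to 96, vitamin E results are blinded only for the first 96 weeks, and Table A.1 ends at week 96. Against this, the footnote letter is not on the EOS/ET cell, and 7.1.2.6 lists the draw explicitly. Blinding to week 96 does not mean that sampling stops there. Table A.1 is not a strict copy of the footnote either, since it also has a week 36 vitamin E window. What stands is that the protocol conflicts with itself. If no end-of-study sample was in fact drawn, only that conflict and the week 264 label remain.

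Second, an end-of-study vitamin E table is inferred. Vitamin E is not a listed endpoint, Appendix A speaks of selected endpoints, and the only SAP analysis section that names vitamin E is the baseline one (10.4). Protocol Table 3 also contains FSH and serum hCG, so pointing to it does not prove that every analyte needs a final-visit summary. This lowers the importance. But SAP 10.7.1 together with a dedicated vitamin E window column puts the analyte in the by-visit summaries.

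Third, for a completer with a normal week 96 sample, the week 96 summary is correct and only the later value is lost. That is right. Contamination needs either a missing week 96 record or the apheresis situation. A programmer would probably settle an apheresis-day tie by closeness to the target, but the text does not say so.

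Fourth, open last windows are usual in this SAP, and Table A.3 is by title for items collected only at end of study. Both explain the omission; neither supplies a window.

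Fifth, a day 756 cap leaves a late unscheduled sample without a window. The midpoint to week 260 would be (673 + 1821)/2 = 1247, giving 589–1246. That still lets a value 1246 − 673 = 573 days late count as week 96, so the tighter cap is preferable, but the choice is the sponsor's.

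**Conclusion.** The point holds and is minor. As written, Appendix A cannot produce an end-of-study vitamin E summary, and a week 260 value can appear only as a week 96 value, 1148 days off target. This rests on the end-of-study draw having taken place, as 7.1.2.6 requires. The number of subjects affected cannot be derived from the documents.

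The week 264 label is 28 days late and clerical. It loses no on-time visit, assuming the ±7 days of the quarterly visits also applies to the final visit, for which 7.1.2.6 states no window. The 28-day target shift could matter only for a subject with more than one record in that window.

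The study is descriptive. The primary adverse-event endpoint, antibody incidence and on-time lipid values are unaffected.

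**What to change.** 1. **Week 96 vitamin E window:** close it, for example at days 589–756, and state that later samples not from an EOS/ET visit are listed only.
2. **End-of-study vitamin E row:** add one assigned by the EOS/ET visit label instead of by study day. Show week 260 completers, identified from disposition, apart from early terminations. State whether an early-termination record may also fill the week window it falls in.
3. **Apheresis rule:** with the cap in place, an end-of-study sample at week 260 can no longer displace a week 96 sample. A short sentence naming the tie-break for two apheresis-day records in one window would complete the rule.
4. **Final visit in Tables A.1 and A.2:** replace week 264 with week 260 (day 1821). Week 252 becomes days 1723–1792 and week 260 becomes day 1793 onward. Antibody Year 4 becomes days 1261–1624 and Year 5 becomes day 1625 onward. An open upper end is harmless here because nothing is scheduled later.
5. **Protocol Appendix A:** reconcile the vitamin E footnote in all three schedules with 7.1.2.6 and the EOS/ET column.

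**Cost:** edits to SAP Appendix A and the visit-mapping program, and a one-line protocol clarification. No new data are needed. An example in protocol 12.3 indicates that results carry an early-termination visit label, and SAP 10.2 already summarizes completion.
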